11.3 HCRN Requirements for Reporting SAEs to Merck

HCRN will report all SAEs to Merck **within 1 business day** of receipt of the SAE/ECI Submission Form from a site. Follow-up information will be provided to Merck as it is received from site. Merck Global Safety (Attn: Worldwide Product Safety; [contact]).

11.4 Sponsor-Investigator Responsibilities

HCRN will send a SAE summary to the sponsor-investigator **within 1 business day** of receipt of SAE Submission Form from a site. The sponsor-investigator will promptly review the SAE summary and assess for expectedness and relatedness.

11.5 HCRN Responsibilities to FDA

For protocols exempt from the requirements of an IND, the above stated requirements are not applicable. HCRN will continue to facilitate compliance of applicable requirements for the sponsor-investigator in relation to this study. This includes but is not limited to 21 CFR 50.20 informed consent, 21 CFR Part 56 IRB, and pertinent sections of the Public Health Service Act and FDAAA.

12. STATISTICAL METHODS

12.1 Study Design

This is a proof-of-principle single-arm phase 2 study in patients with previously treated CUP. All patients receive pembrolizumab combined with RT to a metastatic site, so as to induce an abscopal tumor response. The treatment combination will be repeated with RT delivery to a second metastatic site in a non-overlapping RT field.

The results will be compared with historical control. The primary endpoint is the confirmed response rate (RR) in a non-irradiated site based on best responding abscopal lesion. This study will also evaluate the following secondary endpoints: RR in a non-irradiated site based on RECIST 1.1, adverse events, progression-free survival (PFS), overall survival (OS), time-to-progression (TTP), and disease control rate (DCR).

12.2 Endpoints

12.2.1 Definition of Primary Endpoint

The primary endpoint for this study will assess the confirmed response rate in the best responding abscopal lesion in a non-irradiated site. Best abscopal response is defined as the frequency of patients whose best responding abscopal lesion demonstrates at least a 30% decrease in its longest diameter from baseline (Golden et al., 2015). Responses need to be confirmed (2 consecutive responses at least 4 weeks apart) to count as a response (see Section 11). All eligible patients who are registered and start treatment will be evaluable for response.

The study is powered based on the confirmed response rate. In the largest second-line CUP trials where patients received cytotoxic therapy, patients received gemcitabine alone (N = 39) (Hainsworth et al., 2001) or gemcitabine plus irinotecan (N = 40) (Hainsworth et al., 2005). RRs were 8% and 10%, PFS was not reported, and OS was 3 months and 4.5 months—all respectively.

A Simon's optimal two-stage design will be utilized (see below). This design has 80% power to test the hypothesis of 15% improvement in RR (i.e. 24%) from a historical control of 9%, at one-sided significance level of 0.10. The 2-stage design details are below, where accrual will continue during the interim analysis phase unless we observe a much higher than expected accrual rate or toxicity rate.

Interim Analysis: Enroll 14 eligible patients. If at least 2 confirmed responses are observed in the first 14 eligible patients, we will continue the trial to the second stage and continue the study to a full accrual of 29 eligible patients. Otherwise, the study will be permanently closed due to lack of efficacy.

Final Analysis: If the trial is a success during the interim analysis, we will enroll another 15 eligible patients to the second and final stage (29 eligible total). If at least 5 confirmed responses are observed in the first 29 eligible patients (17%), the treatment will be considered worthy of further investigation. Otherwise, the study will be permanently closed due to lack of efficacy.

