1.2.2.3 Abscopal Response Rate

Importantly, primary endpoint in the NYU trial was the abscopal response rate (defined above), not RECIST 1.1. However, interestingly, a significantly better overall survival was noted in the patients with abscopal responses compared with those without an abscopal response: median overall survival was 21.0 (95% CI 11.1 - 31.0) months for abscopal responders vs 8.3 (95% CI 5.0 – 13.3) months for non-responders (HR 2.06, 95% CI 1.04 – 4.11). Median follow up was 5.6 years. A correlation between abscopal response rate and response per RECIST 1.1 was not reported.

The abscopal response rate, as defined in the NYU study, does not distinguish between nodal and non-nodal lesions. In our study, we will use RECIST criteria for defining a measurable or target lesion, which distinguishes between nodal and non-nodal lesions.

The limitations of standard RECIST in measuring benefit from immunotherapies are increasingly recognized. A significant number of patients have mixed responses (ie, some lesions shrink while others enlarge or remain stable). It is possible that the abscopal response rate may be a better predictor of long-term outcome than RECIST 1.1 when studying the combination of PD-1 inhibition and RT. The risk of relying on RECIST 1.1 alone is that potentially benefitting patients may be overlooked. Our purpose in this small phase 2 trial is to examine this issue in more detail. In addition, our trial will use irRECIST for determination of progression.

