9.4 Measurement of Effect per RECIST 1.1

9.4.1 Target Lesions & Target Lymph Nodes

Measurable lesions up to a maximum of 5 lesions, representative of all involved organs, should be identified as “Target Lesions” and recorded and measured at baseline. Lesions to be monitored for assessment of response must lie outside the RT field. These lesions can be non-nodal or nodal, where no more than 2 lesions are from the same organ and no more than 2 malignant nodal lesions are selected. **NOTE:** If fewer than 5 target lesions and target lymph nodes are identified (as there often will be), there is no reason to perform additional studies beyond those specified in the protocol to discover new lesions.

Target lesions and target lymph nodes should be selected on the basis of their size, be representative of all involved sites of disease, but in addition should be those that lend themselves to reproducible repeated measurements. It may be the case that, on occasion, the largest lesion (or malignant lymph node) does not lend itself to reproducible measurements in which circumstance the next largest lesion (or malignant lymph node) which can be measured reproducibly should be selected.

Baseline Sum of Dimensions (BSD): A sum of the longest diameter for all target lesions plus the sum of the short axis of all the target lymph nodes will be calculated and reported as the baseline sum of dimensions (BSD). The BSD will be used as reference to further characterize any objective tumor response in the measurable dimension of the disease.

Post-Baseline Sum of the Dimensions (PBSD): A sum of the longest diameter for all target lesions plus the sum of the short axis of all the target lymph nodes will be calculated and reported as the post-baseline sum of dimensions (PBSD). If the radiologist is able to provide an actual measure for the target lesion (or target lymph node), that should be recorded, even if it is below 0.5 cm. If the target lesion (or target lymph node) is believed to be present and is faintly seen but too small to measure, a default value of 0.5 cm should be assigned. If it is the opinion of the radiologist that the target lesion or target lymph node has likely disappeared, the measurement should be recorded as 0 cm.

The minimum sum of the dimensions (MSD) is the minimum of the BSD and the PBSD.

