9.5 Response criteria per best abscopal response

A novel aspect of this study is the examination of best abscopal response. Response criteria per best abscopal response are identical to RECIST-defined response criteria, with the exception that tumor shrinkage by > 20% in only a single representative measurable lesion (not a sum of lesions) is sufficient to count as a best abscopal response. In addition, up to 10 measurable lesions per organ may be recorded. Best abscopal response is a binary variable: present or not present. A subject can experience a best abscopal response at the same time as CR, PR, SD, or PD as defined by irRECIST/RECIST 1.1.

See 9.2.2 for guidance on management of cases when a best abscopal response co-occurs with PD as defined by irRECIST/RECIST 1.1.

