9.6 Response Criteria per RECIST 1.1

All target lesions and target lymph nodes followed by

- CT/MRI/PET-CT/Chest X-ray/physical examination must be measured on re-evaluation. Specifically, a change in objective status to either a PR or CR cannot be done without re-measuring target lesions and target lymph nodes.

NOTE: Non-target lesions and non-target lymph nodes should be evaluated at each assessment, especially in the case of first response or confirmation of response. In selected circumstances, certain non-target organs may be evaluated less frequently. For example, bone scans may need to be repeated only when complete response is identified in target disease or when progression in bone is suspected.

Evaluation of Target Lesions

- Complete Response (CR): All of the following must be true:
 - Disappearance of all target lesions.
 - Each target lymph node must have reduction in short axis to <1.0 cm.
- Partial Response (PR): At least a 30% decrease in PBSD (sum of the longest diameter for all target lesions plus the sum of the short axis of all the target lymph nodes at current evaluation) taking as reference the BSD.
- Progression (PD): At least one of the following must be true:
 - At least one new malignant lesion, which also includes any lymph node that was normal at baseline (< 1.0 cm short axis) and increased to \geq 1.0 cm short axis during follow-up.
 - At least a 20% increase in PBSD (sum of the longest diameter for all target lesions plus the sum of the short axis of all the target lymph nodes at current evaluation) taking as reference the MSD (Section 11.41). In addition, the PBSD must also demonstrate an absolute increase of at least 0.5 cm from the MSD.
 - See Section 11.1 on incorporation of irRECIST in determining whether PD on RECIST counts as true progression.

- See Section 11.32 for details regarding the requirements for PD via FDG-PET imaging.
- Stable Disease (SD): Neither sufficient shrinkage to qualify for PR, nor sufficient increase to qualify for PD taking as reference the MSD.

Evaluation of Non-Target Lesions & Non-target Lymph Nodes

- Complete Response (CR): All of the following must be true:
 - Disappearance of all non-target lesions.
 - Each non-target lymph node must have a reduction in short axis to <1.0 cm.
- Non-CR/Non-PD: Persistence of one or more non-target lesions or non-target lymph nodes.
- Progression (PD): At least one of the following must be true:

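### The one-sided 0.10 error rate in 12.2.1 rests on a 9% null from chemotherapy response rates that has not been established for the confirmed best-single-lesion endpoint

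*Combined protocol and SAP*

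**What the plan says.** Section 12.1 describes a single-arm, proof-of-principle phase 2 trial whose results will be set against historical control. Section 12.2.1 makes the primary endpoint a response in the best responding non-irradiated lesion, confirmed by two consecutive responses at least 4 weeks apart. It then cites two second-line chemotherapy trials, gemcitabine alone (N = 39) and gemcitabine plus irinotecan (N = 40): "RRs were 8% and 10" per cent respectively. The design statement follows: "This design has 80% power to test the hypothesis of 15% improvement in RR (i.e. 24%) from a historical control of 9" per cent, at one-sided 0.10. The rule is to continue if there are at least 2 responses in 14 patients and to declare success if there are at least 5 in 29.

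Elsewhere the plan treats best-lesion response and RECIST response as different measures:

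- **RECIST partial response (9.6):** "At least a 30% decrease in PBSD (sum of the longest diameter for all target lesions plus the sum of the short axis" of the target nodes. Target lesions are limited in 9.4.1: "Measurable lesions up to a maximum of 5 lesions, representative of all involved organs".
- **Best abscopal response (9.5):** shrinkage "in only a single representative measurable lesion (not a sum of lesions) is sufficient to count as a best abscopal response"; "up to 10 measurable lesions per organ may be recorded"; and "A subject can experience a best abscopal response at the same time as CR, PR, SD, or PD as defined by irRECIST/RECIST 1.1".
- **Link between the two (1.2.2.3), for the model trial of radiotherapy plus GM-CSF:** "A correlation between abscopal response rate and response per RECIST 1.1 was not reported".

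**The concern.** A one-sample test has its nominal error rate only if the null describes the endpoint being tested. Here the null comes from response rates reported for chemotherapy, while the test counts patients with one responding lesion. A patient whose lesions respond unevenly, or who has RECIST progression, can count as a success on the second measure without being a responder on a sum-based one.

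The stated 0.10 is the chance of a false success only if the historical chemotherapy would also have produced 9% confirmed best-lesion responses. The chance of stopping at stage 1 carries the same condition. Section 12.2.1 gives the 0.10 without this qualification, and 12.1 announces a comparison with historical control. At stake is what 5 responses in 29 patients can be said to show.

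**Working it through.** **Inputs.** From 12.2.1: p0 = 0.09, p1 = 0.24, one-sided 0.10, power 80%, n1 = 14 (continue if ≥ 2), n = 29 (success if ≥ 5), historical rates 8% (N = 39) and 10% (N = 40).

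**1. Where the 9% comes from.** The text does not spell out the step, but these are the only rates beside it. Weighted by N: (0.08 × 39 + 0.10 × 40)/79 = 7.12/79 = 9.0%.

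**2. Reproducing the design.** With X1 ~ Bin(14, p) and X2 ~ Bin(15, p),

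P(success) = Σ over x = 2 to 14 of P(X1 = x) × P(X2 ≥ 5 − x).

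At p = 0.09:

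- x = 2: 0.2377 × 0.1469 = 0.0349
- x = 3: 0.0940 × 0.3965 = 0.0373
- x = 4: 0.0256 × 0.7570 = 0.0194
- x ≥ 5: 0.0059

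The total is 0.0975. At p = 0.24 the same sum gives 0.8058. Stage 1 stopping at 9% is 0.91^14 + 14 × 0.09 × 0.91^13 = 0.2670 + 0.3698 = 0.637. An exhaustive search (n ≤ 45) returns this same rule as the Simon optimal design, with expected N under the null of 14 + 15 × (1 − 0.637) = 19.4. The plan's arithmetic is right.

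**3. The same rule at other nulls.** Here p is the rate that the historical treatment would give on the confirmed best-lesion scale.

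| p | P(success) | P(stop at stage 1) |
|---|---|---|
| 8% | 0.066 | 0.69 |
| 9% | 0.097 | 0.64 |
| 10% | 0.136 | 0.58 |
| 12% | 0.229 | 0.49 |
| 15% | 0.393 | 0.36 |

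P(success) reaches 0.10 at p of about 9.07%. The 12% and 15% rows are assumptions; the documents give no such rates.

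**4. Direction on one scan.** Take the same lesions and axis and a 30% threshold. If every lesion shrinks by less than 30%, each follow-up diameter exceeds 0.7 times its baseline, so the sum exceeds 0.7 times its baseline. A 30% fall in the sum therefore requires at least one lesion to fall by 30%, and the best-lesion rate cannot be below the sum-based rate. With one assessable lesion the two are equal. Inclusion criterion 8 asks for only one measurable lesion outside the RT fields, so such patients can be enrolled.

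**5. Direction after confirmation.** Take two 20 mm lesions measuring 10 and 18 mm at scan 1, then 18 and 10 mm at scan 2. The sum is 28 of 40 mm both times, a confirmed 30% fall, yet neither lesion reaches 30% twice in a row. If the same lesion must confirm, which the plan does not say, the ordering is not guaranteed. The example is extreme, but it limits the result in step 4 to a single scan.

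**6. Sampling error in the null.** If the cited rates are 3/39 and 4/40 (assumed from rounding), the pooled rate is 7/79 = 8.9%, exact 95% CI 3.6% to 17.4%. This uncertainty would remain with a matched endpoint.

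**The case against.** The strongest reply has four parts.

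**Every single-arm error rate is conditional on its null.** This stands. The two cited rates alone move the error from 0.066 to 0.136, so the table in part shows ordinary sensitivity. What is particular here is an unacknowledged change of measure between the null and the test.

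**The documents do not show that 9% is too low.** This also stands. A reader might infer that the true error rate is well above 0.10. The documents do not support that. The historical criteria and confirmation rules are not given, and confirmation or a single assessable lesion may reduce or remove any excess. The mixed responses described in 1.2.2.3 concern immunotherapy, not chemotherapy, and the unreported correlation there concerns only the model trial. Its 27% best-lesion rate (1.2.2.2) comes from another treatment and mostly lung and breast cancer, so it cannot serve as a null.

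**The null could even be conservative.** If it is meant as the rate under inactive treatment, a figure from active chemotherapy might be high. For that reason the null is defined here as the rate the historical treatment would give on the tested scale.

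**The plan claims little.** Success means only that the treatment merits further study, 1.6 leaves confirmation to randomized trials, and RECIST 1.1 response is already a secondary endpoint. A reader might infer that the trial claims superiority to chemotherapy; nowhere does it say so. This lowers the severity. It does not supply the missing condition on the 0.10.

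**Conclusion.** The concern holds as a point about comparability that has not been established. The 0.10 is valid only if the historical chemotherapy would give 9% on the confirmed best-single-lesion endpoint, and nothing in the documents shows that it would. It would be wrong to infer a miscalculated design: 0.0975 at 9% and 0.806 at 24% are correct, and power at a true 24% does not depend on the null. There is almost no margin, however, since the error passes 0.10 at about 9.07%.

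The size of any excess in the null cannot be fixed from the documents and, for confirmed response, neither can its direction. The single-scan ordering assumes the same lesions, the same axis and a 30% threshold. Severity is minor to moderate, because the issue is how the error rate is stated and what a success is said to show.

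**What to change.** **First** reconcile the best-lesion threshold. It is at least 30% in 12.2.1 and for non-nodal lesions in 9.2.1, more than 20% in 9.5, and has no percentage for nodal lesions in 9.2.1. Until that is settled, a best-lesion rate has no fixed meaning.

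**Then**, keeping the endpoint, sample size and rule (≥ 2/14, ≥ 5/29):

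- **12.2.1:** state that the 9% is taken from response rates in two chemotherapy trials and has not been established for a best-lesion endpoint. Give the chance of success as 0.066, 0.097, 0.136, 0.229 and 0.393 if the rate the historical treatment would give on the confirmed best-lesion scale is 8, 9, 10, 12 and 15%.
- **12.1 and synopsis:** state that meeting the rule is proof of principle and not a like-for-like comparison with the 9%.
- **Secondary analysis:** report the planned RECIST 1.1 response rate in non-irradiated lesions with an exact 95% CI beside the 9%. It is the closer comparison but descriptive only. Note that the historical criteria are not given and that it plays no part in the go/no-go decision.

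**Cost.** The changes are wording plus one confidence interval. The stated error rate looks less favourable, and the RECIST comparison is imprecise: 3/29 = 10.3% has an exact 95% CI of 2.2% to 27.4%. The interval still includes 9% at 6/29 (8.0% to 39.7%) and first excludes it at 7/29 (10.3% to 43.5%). P(X ≥ 7 of 29) at a true 24% is 0.56, against 0.81 for the current rule, which is why it should stay outside the decision.

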12.2.2 Definition and Analysis of Secondary Endpoints

- Response rate (RR) by RECIST 1.1.
- Adverse events: The maximum grade for each type of adverse event will be summarized using CTCAE version 4.0. The frequency and percentage of grade 2+ adverse events will be assessed. We will also explore the treatment related adverse events as well (toxicities).
- Progression-free survival (PFS) is defined as the time from registration to the first of either disease progression or death from any cause, where disease progression will be determined based on RECIST 1.1 criteria. PFS will be estimated using the Kaplan-Meier method, where patients that are alive and progression-free will be censored on their last tumor evaluation date.
- Overall Survival (OS) is defined as the time from registration to death from any cause. OS will be estimated using the Kaplan-Meier method.
- Time-to-Progression (TTP) is defined as the time from registration to disease progression, where patients that are progression-free will be censored on their last tumor evaluation date. TTP will be estimated using the cumulative incidence method, where deaths will be treated as competing risks.
- Disease Control Rate (DCR) is defined as the frequency (%) of patients who have a best response of PR, CR, or Stable disease.
- The association between RR (using RECIST 1.1 (informed by irRECIST)) with other clinical endpoints (e.g., OS, PFS, etc.) will be performed. For time-to-event endpoints, we will use Cox proportional hazards models and Kaplan-Meier methodology. This analysis of RR as a predictor of OS, PFS, etc. will be based on a landmark analysis at various time points of interest post-baseline that correspond to expected tumor assessment time points. This will eliminate the possible response bias of patients living longer or doing better because they lived long enough to respond to treatment. For any associations of RR with categorical data, we will use Chi-square or Fisher's exact tests along with logistic regression models. Descriptive statistics and graphical techniques will be used to summarize this data. Given the small sample size, all these analyses will be considered hypothesis generating and exploratory.

12.3 Sample Size and Accrual

A maximum of 29 evaluable patients will be accrued onto this phase II study unless the study is closed early for excessive toxicity or lack of efficacy. To account for potential ineligibles, major treatment violations during Cycle 1, or cancellations, we will enroll an additional 5 patients, for a total of 34 patients. The expected accrual rate is about 1.5 patients per month across the Hoosier sites. With this accrual rate, we expect to finish accrual within about 23 months, assuming we accrue 34 total patients. We anticipate that the study will take approximately 36 months to complete. This allows a 9-month follow-up for the final patient enrolled, along with data entry, data clean-up, and analysis. Given the expected accrual rate is around 1.5 patients per month, it is expected that the study will take around 23 months to fully accrue. We plan to monitor the accrual continually and if we only end up accruing 6 patients or less in the first year (after study activation), we will consider stopping the trial for slow accrual.

12.4 Assessment of Safety

Any subject who receives at least one dose of treatment on this protocol will be evaluable for toxicity. The National Cancer Institute (NCI) Common Terminology Criteria for Adverse Events (CTCAE) v4 will be used. The Study Calendar shows the schedule of toxicity assessments.

12.5 Assessment of Efficacy

All eligible patients who are registered and receive at least one dose of trial drug will be evaluable for all efficacy endpoints.

